4. OUTCOME MEASURES

Primary outcome: Respiratory morbidity, defined as requiring admission to the neonatal nursery and any form of respiratory support (e.g. intermittent positive pressure via an endotracheal tube, nasal continuous positive airway pressure (CPAP), Hi- or Lo-flow oxygen/air mixture, or increased ambient oxygen delivered into an incubator) for ≥ 60 minutes at any time following birth.

Secondary outcomes:

For the infant:

- hypoglycaemia defined as any blood glucose concentration < 2.6 mmol/l;

- hypoglycaemia requiring treatment other than milk feeding (including dextrose gel, intravenous dextrose, glucagon);
- admission to a neonatal nursery and length of stay;
- severity of respiratory distress (severe: any intubation/mechanical ventilation and/or need for surfactant therapy; moderate: respiratory support (sum of mechanical and non-invasive) required for >24 hours; mild: the remainder requiring respiratory support for ≥60 minutes but <24 hours). The maximum appropriate mean airway pressure [MAP] for those requiring mechanical ventilation or nasal CPAP, and maximum appropriate fractional inspired oxygen [FiO₂] for those requiring any form of respiratory support will also be recorded. For those on HiFlo, the maximum appropriate flow rate will be recorded.
- need for, and duration of, all forms of respiratory support (including all forms of respiratory support described in the primary outcome);
- use of exogenous surfactant;
- pneumothorax or air leak requiring drainage;
- presence of x-ray features suggestive of hyaline membrane disease or transient tachypnoea of newborn (independently adjudicated by a neonatal radiologist blinded to treatment allocation) in a subset of babes who require chest x-ray as part of clinical care.

For the mother:

- requirement for additional insulin therapy after administration of study drug;
- requirement for hospital admission between randomisation and CS;
- highest blood glucose concentration recorded between randomisation and birth;
- maternal infection from the time of randomisation up until 6 weeks' postpartum including chorioamnionitis; maternal pyrexia ≥38°C; wound infection requiring antibiotic or surgical /radiological (e.g. ultrasound-guided drainage) treatment;
- maternal reported side effects of the study drug;
- maternal mental health assessed using the Edinburgh Postnatal Depression scale (EPDS);^{56,57}

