5.1 STUDY TYPE & DESIGN & SCHEDULE

The PRECeDe Randomised Trial is an international multicentre, randomised, triple blind, placebo controlled trial (Figure 4).

Trial setting: The trial will be conducted in maternity units throughout Australia and New Zealand

Trial entry: Women will be identified and counselled by trained research midwives. Written consent will be obtained. In accordance with the CONSORT statement⁶⁰ we will collect data regarding the number of eligible participants, the number approached, and the number of participants who decline to take part in the trial via a waiver of consent to collect deidentified data regarding potentially eligible participants.

Randomisation: Eligible, consenting women will be randomised using a computer generated random number sequence. The randomisation schedule, using a 1:1 randomisation and variable block size will be prepared in advance.

Randomisation will be stratified by:

- Type of diabetes (Type 1 diabetes, Type 2 Diabetes, Gestational Diabetes)
- Gestation at delivery (35⁺⁰ to 36⁺⁶ and 37⁺⁰ to 38⁺⁶ weeks, 39⁺⁰ to 39⁺⁶ weeks)
- Recruiting site

Randomisation can only take place within 7 days prior to planned elective CS and at least 24 hours prior to planned elective CS to allow two doses of betamethasone to be administered prior to birth. Randomisation can occur within the week prior to 35⁺⁰ weeks gestation as long as the planned CS is scheduled after 35⁺⁰ weeks gestation.

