Treatment Allocation: Assignment is to either the 'betamethasone group' or the 'placebo group'. A study number will be allocated to the participant that corresponds to the relevant trial treatment pack, each of which look identical and contain two masked syringes each containing either 11.4 mg of Celestone Chrondose in 2 ml (betamethasone 11.4 mg, as betamethasone sodium phosphate and betamethasone acetate) or placebo (normal saline 2 ml), both of which will be supplied and packaged by Baxter Healthcare Corporation who have confirmed stability testing for both the active drug and placebo for 180 days. Syringes will be masked with red tape to ensure that the volume of contents can be assessed but the betamethasone suspension will not be distinguished from the clear solution of the placebo. The syringes will be packaged with the appropriate randomisation number by Zeullig Pharma. All drugs will be prescribed by a medical practitioner as "Betamethasone 11.4mg in 2 ml, x2 doses or Normal Saline Placebo 2 ml, x 2 doses" and dispensed by Pharmacy staff at the recruiting site according to the allocated randomisation number.

Treatment schedules: Women in both treatment groups will be given the contents of one of their allocated syringes intramuscularly at least 24 hours prior to the planned CS. The second injection will be retained at the site and administered 24 hours (\pm 4 hours) later. Researchers, participants and staff will be blinded to the treatment allocation. If birth is required less than 24 hours after the first injection (for example, if the CS time must be brought forward due to maternal or fetal issues (eg spontaneous onset of labour), the second injection will be withheld. The reasons for not administering the second injection will be recorded on the CRF. The second injection should not be given earlier than 20 hours after the first injection. Failure to administer the second injection does not constitute withdrawal from the trial. There is no minimum amount of time required between the second injection and the CS.

If the CS is delayed beyond 7 days following administration of the two injections, repeat study medication (or antenatal corticosteroids) should not be administered.

Standard Care: Care for both groups will otherwise be according to standard practice for women with diabetes and their infants.

Monitoring of maternal blood sugars and treatment of maternal hyperglycaemia

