All participants will be instructed to monitor their blood glucose using a capillary blood glucose monitor prior to every meal and 2 hours following meals for 72 hours after the first injection. Participants will be asked to record all blood glucose readings via REDcap with the link provided at the time of randomisation. Women who normally use continuous glucose monitoring or flash glucose monitoring should be advised to use capillary blood glucose monitoring according to the above schedule during this time period in addition to their continuous or flash blood glucose monitor. All participants will be provided with a site specific information sheet which will provide information about target blood sugars and what to do in the event of hypoglycaemia or hyperglycaemia. Women who experience hyperglycaemia will be advised to contact

the relevant staff at the participating site for advice regarding insulin titration. Maternal hyperglycaemia will be managed in accordance with local protocols with the aim being to ensure euglycaemia as much as possible. Staff who provide advice regarding the management of hyperglycaemia will be encouraged not to disclose whether they suspect the participant receive bethamethasone or placebo. Guidance regarding insulin management is provided in the PRECeDe Insulin Management Guideline (see Appendix 2) however relevant staff at each site will be responsible for individualising the care.

While, there is no requirement for women who are otherwise well to be admitted during the period between randomisation and the CS, individual sites may choose to arrange routine admission for close surveillance if that is their usual practice. Admission for close surveillance is recommended in the event of significant maternal hyperglycaemia or hypoglycaemia.

Monitoring of neonatal blood glucose and treatment of neonatal hypoglycaemia

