Neonatal care for all infants will be in accordance with local protocols for the management of infants born to women with diabetes. At a minimum, all infants will undergo blood glucose testing (preferably using a glucose oxidase method (eg i-STAT or blood gas analyser) within the first 2 hours of life and then every 3-4 hours until 3 consecutive blood glucose recordings $>2.6\text{mmol/L}$. Further management including the treatment of hypoglycaemia and the timing of subsequent blood glucose measurements will be determined according to the local site algorithms. Where a site does not have a local algorithm, we recommend that Australian sites follow the Safer Care Victoria algorithm (Appendix 3) and New Zealand sites follow the Auckland DHB algorithm (Appendix 4)

Concomitant Medications / Treatments: All concomitant medications received by both the mother following randomisation, and the infant following birth, up until the time of discharge home following birth will be recorded. There are no restrictions regarding concomitant medications except antenatal corticosteroids (which constitute an exclusion criterion if received at any time before randomisation).

Compliance: Compliance with the allocated treatment schedule will be recorded, however as analysis will be by intention to treat, non-compliance with the allocated treatment schedule (including failure to complete the two injections) will not be regarded as an indication for exclusion or withdrawal from the trial.

Assessment of Blinding: The ability to retain blinding will be assessed in a subset of the participants if required (see section 7.4 Trial Risks). The following participant staff groups will be asked to predict which group the participant was allocated to (Betamethasone or Placebo or uncertain).

and their reason for this

- Participants
- Any staff members providing care for the participant or her baby
- Research staff involved in collection of outcome data

Data Collection: Prior to discharge following birth, participants will be asked by the site research team to complete a questionnaire about any side effects following trial medication administration. This will include questions regarding a range of symptoms including pain at the site of injection, flushing, fatigue, nausea, headaches, visual changes, changes in fetal movement patterns, hyperglycaemia, hypoglycaemia and adjustments to insulin doses.

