6. STUDY POPULATION

6.1 INCLUSION CRITERIA

Pregnant women with a singleton or twin pregnancy who have pre-gestational diabetes OR gestational diabetes.

AND

plan to give birth by elective CS between 35⁺⁰ and 39⁺⁶ weeks gestation (randomisation can occur within the week prior to 35⁺⁰).

AND

The CS is scheduled between 24 hours and 7 days from the time of randomisation.

Pre-gestational diabetes is defined (for the purposes of this trial) as either Type 1 or Type 2 diabetes that was diagnosed prior to the start of the pregnancy (regardless of whether the patient received medication for the diabetes prior to the start of the pregnancy).

Gestational diabetes is defined in Australia as an abnormal pregnancy 75 g Oral glucose tolerance test according to the WHO criteria for gestational diabetes.⁶¹ Gestational diabetes is defined in New Zealand according to the Ministry of Health.⁶² Gestational diabetes may also be diagnosed in either country via the modified criteria for diagnosis of gestational diabetes during the COVID-19 pandemic recommended by Royal Australian New Zealand College of Obstetricians and Gynaecologists and Australasian Diabetes in Pregnancy Society.⁶³

WHO criteria for diagnosis of gestational diabetes or diabetes in pregnancy⁶¹ :

- a) Gestational diabetes mellitus should be diagnosed at any time in pregnancy if one or more of the following criteria are met:
 - fasting plasma glucose 5.1-6.9 mmol/l
 - one hour plasma glucose \geq 10.0 mmol/l following a standardised 75g oral glucose load
 - two hour plasma glucose 8.5-11.0 mmol/l following a 75g oral glucose load

- b) Diabetes mellitus in pregnancy should be diagnosed if one or more of the following criteria are met⁶¹ (however for the purposes of this trial, these participants will be classified as gestational diabetes):
 - fasting plasma glucose \geq 7.0 mmol/l
 - two hour plasma glucose \geq 11.1 mmol/l following a 75g oral glucose load
 - a random plasma glucose \geq 11.1 mmol/l in the presence of diabetes symptoms

New Zealand Ministry of Health⁶² criteria for gestational diabetes:

- fasting plasma glucose ≥ 5.5 mmol/L
- two hour post-prandial plasma glucose ≥ 9.0 mmol/L following a 75g oral glucose load

The modified criteria for diagnosis of gestational diabetes during the COVID-19 pandemic recommended by Royal Australian New Zealand College of Obstetricians and Gynaecologists and Australasian Diabetes in Pregnancy Society:⁶³

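### The maternal peak-glucose outcome starts at randomisation, up to about 6 days before any study drug, while the protocol's glucose monitoring starts at the first injection

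*Protocol*

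**What the plan says.** Protocol section 5.1 (Randomisation) gives the window: "Randomisation can only take place within 7 days prior to planned elective CS and at least 24 hours prior to planned elective CS". Section 6.1 repeats it as an inclusion criterion: "The CS is scheduled between 24 hours and 7 days from the time of randomisation". Section 5.1 (Treatment schedules) says that women are "given the contents of one of their allocated syringes intramuscularly at least 24 hours prior to the planned CS". No section limits the time from randomisation to the first injection, and the study table shows the two as separate columns with no interval between them.

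Among the maternal secondary outcomes, section 4 lists the "highest blood glucose concentration recorded between randomisation and birth". Section 5.1 (Monitoring of maternal blood sugars) schedules capillary testing "prior to every meal and 2 hours following meals for 72 hours after the first injection", and asks participants to "record all blood glucose readings via REDcap with the link provided at the time of randomisation". In the study table, the row for glucose and insulin data is first marked under the first dose, with no mark under randomisation. The additional-insulin outcome in section 4 counts only what happens after study drug is given. Hypothesis 3 in section 3.3 is that maternal morbidity, including hyperglycaemia, does not increase.

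**The concern.** The outcome window and the data-collection window do not match. The outcome can cover days on which neither arm has received anything. A maximum is sensitive to this: each extra drug-free reading is another chance for the peak to fall outside the period in which the drug could have acted. When that happens, the drug's contribution to the woman's peak is partly or wholly hidden.

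The window is the same in both arms, so no false difference is created. The error runs toward no difference. For most outcomes that would be conservative. Here the hypothesis is that the drug does not raise maternal hyperglycaemia, so attenuation favours the hoped-for conclusion on a safety question.

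**Working it through.** **1. Length of the drug-free stretch.** Randomisation may be 7 days before the planned CS, and the first injection as late as 24 hours before it: 7 days − 1 day = 6 days.

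**2. Start of each window, side by side.**

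| Item | Starts at | Protocol |
|---|---|---|
| Highest blood glucose | randomisation | section 4 |
| Scheduled capillary testing | first injection (for 72 h) | section 5.1 |
| Collection of glucose and insulin data | first dose | study table |
| Additional insulin outcome | study drug | section 4 |

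The peak-glucose outcome is the odd one out.

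**3. Can pre-dose readings enter?** Yes, though how many is unknown. These women have diabetes and may already be testing. The request is for all readings, through a link supplied at randomisation. The pilot-trial discussion in section 3.2 also plans upload direct from the glucometer, which can carry earlier values.

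**4. Direction.** Let P be a woman's highest recorded pre-dose value, D her highest post-dose value without drug, and δ the drug shift. The effect seen in her maximum is

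max(P, D + δ) − max(P, D).

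This equals δ only when P ≤ D, lies between 0 and δ when D < P < D + δ, and is 0 when P ≥ D + δ. It never exceeds δ, so recorded pre-dose values can only shrink the contrast.

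**5. Size, under assumptions.** The documents give no glucose SD, drug shift or reading frequency. Assumed: within-woman SD 1.2 and between-woman SD 0.6 mmol/L, two post-dose days with six readings a day, and a true shift of 1.5 mmol/L. Simulated difference in mean maximum (mmol/L):

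| Pre-dose readings per day | 1 pre-dose day | 3 days | 5 days |
|---|---|---|---|
| none | 1.50 | 1.50 | 1.50 |
| 1 | 1.46 | 1.39 | 1.32 |
| 2 | 1.41 | 1.28 | 1.19 |
| 6 | 1.28 | 1.04 | 0.90 |

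With a true shift of 1.0 and six pre-dose readings a day, the difference is 0.82, 0.61 and 0.50.

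**6. Primary outcome, for scale.** Section 8.1 plans for 6% versus 3%, two-sided 0.05, 90% power, continuity correction and 3% drop-out. The uncorrected size is [1.96√(2 × 0.045 × 0.955) + 1.2816√(0.06 × 0.94 + 0.03 × 0.97)]² / 0.03² = 1002 per arm. The continuity correction gives 1002/4 × [1 + √(1 + 4/(1002 × 0.03))]² = 1068. Then 1068/0.97 = 1102 per arm, or 2204 in total, which agrees with the stated 2200.

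If a share f of women never receives an injection and keeps the control rate, the treated-arm rate is 0.03 + 0.03f. Continuity-corrected power with 1100 × 0.97 = 1067 per arm:

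| f (assumed) | Treated-arm rate | Power |
|---|---|---|
| 0 | 3.00% | 90.0% |
| 1% | 3.03% | 89.3% |
| 3% | 3.09% | 87.8% |
| 5% | 3.15% | 86.2% |

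**The case against.** The best defence is that few pre-dose values will exist. Testing is scheduled only after the first injection, and the study table collects nothing earlier, so in practice the outcome may already be a post-dose maximum. This stands as a limit on size: with no pre-dose readings there is no loss, and six a day is the adverse end of the range. It does not rescue the definition, which would then describe a window in which the protocol collects no data.

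Second, this is one secondary outcome, and the insulin outcome, already anchored to study drug, captures clinically important hyperglycaemia. That is fair and keeps the point modest.

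Third, the analysis plan, which is not shown, may set the window precisely. It may, but the protocol's outcome definition should still agree with its own schedule.

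A reader might go further and infer that the open interval damages the primary analysis, because women may give birth before any injection, and that randomisation should therefore move to the injection visit. The documents do not support this:

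- The protocol foresees early birth ("if the CS time must be brought forward due to maternal or fetal issues (eg spontaneous onset of labour"), and its compliance rule is that "non-compliance with the allocated treatment schedule (including failure to complete the two injections) will not be regarded as an indication for exclusion or withdrawal". Keeping never-injected women is correct under intention to treat.
- No non-receipt rate is given. The shares in step 6 are assumed, and some non-receipt would occur without any gap.
- Section 8.1 rests its effect on a trial with RR 0.46 but powers for 0.50. If 0.46 held in treated women, the diluted RR would be 0.46 + 0.54f, reaching 0.50 only at f = 0.04/0.54 = 7.4%. This slack is conditional, because section 8.1 also cites RRs of 0.74 and 0.40.
- Randomising at the injection visit would put allocation, pharmacy dispensing and injection into one sitting, at sites that hold low stock. That is a logistical trade-off for the sponsor.

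**Conclusion.** The peak-glucose outcome is mis-anchored. Its window opens up to about 6 days before study drug and disagrees with the monitoring schedule, the study table and the insulin outcome. Recorded pre-dose readings attenuate the between-arm difference, toward the hypothesis of no increase.

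The direction follows from the definition. The size rests on assumed SDs, an assumed shift and an unknown recording frequency: from no loss at all to a fall from 1.5 to about 0.9 mmol/L in the most adverse case shown, so neither end should be quoted alone. The trial's validity is not in question.

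Possible dilution of the primary effect is a matter to monitor and not an error. At 1% never injected it costs under one point of power.

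**What to change.** In section 4, define the outcome as the highest blood glucose recorded from the first injection to birth or 72 hours after that injection, whichever comes first, in both arms. This matches the monitoring already scheduled. Because injections are blinded, the anchor is comparable between arms.

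Keep women who are never injected in the analysis, starting their window at the planned first-injection time, or at randomisation if none was set. Randomisation should also be the start when birth came before the planned time, since the window would otherwise be empty. If the trial moves to the open-label design in section 8.3, controls receive no injection, so the planned time should then be the anchor in both arms.

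Record the planned first-injection time at randomisation, the interval from randomisation to first injection, and the number never injected by arm, so that any dilution can be seen.

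The cost is a wording change and one or two data fields. The small downside is that readings outside the 72-hour window no longer count toward this outcome. No change to the timing of randomisation or of the injections is needed.

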We assessed the ability for participants, clinicians and research staff to remain blinded to the treatment allocation⁵² and found that while it was possible for some participants to guess their treatment allocation on the basis of the presence or absence of subsequent maternal hyperglycaemia, this was by no means the case for all participants (Table 2) and did not necessarily correlate with staff providing clinical care correctly guessing the treatment allocation. Both the midwife administering the study medication and the midwife collecting the research outcome data demonstrated the highest likelihood of accurately predicting the treatment allocation. In the former group, this was due to the recognition that even though the syringe was mostly masked with the trial identification label, the cloudy betamethasone suspension could still be distinguished from the clear saline solution in the trial syringes. The research midwives collecting the outcome data were able to correctly predict the treatment allocation on the basis of the presence or absence of maternal hyperglycaemia when the participant blood glucose monitoring logs were collected at the time of CS. While the blinding of participants was less optimal than we had hoped, the fact that clinicians providing postnatal care could remain blinded provides a justification to proceed with a double blinded study since it will be these clinicians who will make the decisions regarding patient care (maternal and neonatal) which form the basis of our primary and key secondary outcomes. We have also identified strategies to improve the syringe masking to ensure that staff administering the study medication would remain blinded. Preventing research midwives from collecting maternal blood sugar data by having participants upload these themselves (direct from their glucometer) will also help to maintain blinding of research personnel involved in the collection of outcome data.

As part of the pilot trial, a qualitative assessment of participant (n=13) and staff perspectives (n=10) of the trial was undertaken. All participants confirmed that they felt very well informed about the trial, found it highly acceptable, and an important topic to study. Likewise, interviews with staff indicated great confidence that the trial benefits outweighed the risks, and that this was an important trial to generate robust evidence to guide practice.

Table 2: Assessment of participant and staff blinding to treatment allocation

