After discharge of the mother and baby from hospital after the birth, the health outcome data will be collected from the case records by the research midwife at the recruiting centre and entered into a purpose built REDCap database.

Women and their children will be followed up after discharge from hospital with questionnaires regarding additional maternal morbidity (wound infections, mental health) and neonatal morbidity (respiratory illness, method of feeding, and feeding difficulties) completed at 6 weeks' postpartum. In addition we will collect health information via the standardised SF12, EPDS and the AQoL-8D. Women who score ≥ 13 on the EPDS will be contacted by the lead investigator / trial coordinator at the respective site to assess maternal well being and will be directed to appropriate resources according to local guidelines.

All data will be entered into a REDCap database stored on a secure password protected server at The University of Melbourne.

Childhood Follow-Up: We will seek permission for on-going contact at least annually with mothers and their infants as part of the consent process. This contact will take the form of an email message with an annual 'birthday card' sent to the email address as well as an SMS request to update participant contact details. Future childhood follow-up studies are planned and separate funding will be sought to undertake these studies. All future studies will require HREC approval.

Emergency Unblinding: Unblinding is unlikely to be required for management of a participant with an adverse event as the effect of antenatal corticosteroids is generally short lived. However, emergency unblinding will be possible and can be arranged by contacting the Trial Coordinator or Coordinating Principal Investigator.

STUDY TABLE

Procedures	Assessment / Procedure	Screening (after 32 weeks)	Randomisation (within 7 days of planned elective CS)	First dose of betamethasone or placebo	Second Dose of Betamethasone or placebo (24 hours after first dose)	Caesarean Section and Post birth visit / data collection	Discharge of mother and baby	6 week follow-up	Annual follow-up
	Informed Consent	X							
	Demographic Information Weight & Height Measurement		X						
	Administration of Betamethasone or placebo			X	X				
	Symptoms questionnaire					X		X	
	Completion of EPDS, SF12, AQuOL 8D		X					X	
	Collection of data about blood glucose measurements and insulin doses			X	X	X			
	Collection of birth and neonatal data					X	X		

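### The only scheduled symptom questionnaires follow the caesarean with no stated pre-caesarean recall window, and they bring the site research team back to the glucose information the protocol means to keep from research midwives

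*Protocol*

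**What the plan says.** **Timing.** Protocol section 5.1 (Data Collection) states: "Prior to discharge following birth, participants will be asked by the site research team to complete a questionnaire about any side effects". The study table in the same section marks the row "Symptoms questionnaire" at the caesarean and post-birth visit and at 6 weeks, and at neither injection. The items cover "a range of symptoms including pain at the site of injection, flushing, fatigue, nausea, headaches", then visual changes, and "changes in fetal movement patterns, hyperglycaemia, hypoglycaemia and adjustments to insulin doses". Section 4 lists side effects reported by the mother among the maternal secondary outcomes.

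**Interval to surgery.** Section 5.1 requires the first injection at least 24 hours before the planned caesarean. The second follows about 24 hours later, with no minimum interval between it and the operation.

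**Blinding.** Section 3.2 (PRECeDe Pilot Trial) reports that research midwives collecting outcomes could tell the allocation from whether the mother had become hyperglycaemic. Table 2 gives their kappa as 0.81 (95% CI 0.54 to 1.00). The stated remedy is "Preventing research midwives from collecting maternal blood sugar data by having participants upload these themselves". Section 5.1 then has the site research team request the symptom form, and says that after discharge "the health outcome data will be collected from the case records by the research midwife at the recruiting centre".

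**The concern.** There are two separate problems.

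First, a form about the effects of an antenatal injection is filled in only after an operation that can itself cause several of the same symptoms. Nothing in the protocol text asks the woman to separate what she felt before the caesarean from what she felt after it. Symptoms common to both arms pull the comparison towards no difference. For a harm outcome that is the unsafe direction, because the study question asks for benefit without adverse consequences for the mother. Section 12.1 does not require adverse events to be reported unless they meet SUSAR or outcome criteria, so this questionnaire is the main scheduled source for non-serious maternal symptoms.

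Second, the protocol identifies the cue that unblinded its pilot outcome collectors and names a safeguard. It then routes a form containing the same cue through the site research team, and has a research midwife at that centre abstract the outcomes. At stake is the blinding of abstraction, including judged items such as the maximum appropriate airway pressure and inspired oxygen recorded with the severity outcome. Section 7.4 also makes research-staff kappa above 0.41 one ground for moving to an open-label design if recruitment or budget problems arise, so an avoidable leak could feed that decision.

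**Working it through.** The protocol gives no figure on this point. The check is a comparison of texts plus an illustration of dilution.

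**1. Number per arm.** For 6% against 3%, 90% power, two-sided alpha 0.05 and continuity correction, I get 1,068 per arm. Allowing for 3% drop-out, 1,068 / 0.97 = 1,101.03, rounded up to 1,102, against the stated 1,100. The sample size reproduces. After drop-out, 1,100 × 0.97 = 1,067 per arm is used below.

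**2. Which items overlap with surgery** (my judgement; the protocol does not classify them).
- Can also follow surgery or anaesthesia: flushing, fatigue, nausea, headache.
- Largely specific to the period from injection to birth: injection-site pain, change in fetal movements, hyperglycaemia and insulin adjustment. Participants also record glucose in REDCap for 72 hours from the first injection.

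**3. Dilution of an overlapping item.** Let p be the probability of the symptom after injection and b an independent probability of the same symptom after surgery, equal in both arms and not separated by time.

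Observed rate = 1 − (1 − p)(1 − b), so the risk difference becomes (1 − b) × (p1 − p0).

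Power = Φ{[d − 1.96 × √(2 × p̄(1 − p̄)/n)] / √[(p0(1 − p0) + p1(1 − p1))/n]}, with n = 1,067 and the observed rates inserted.

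Assumed true rates 15% against 10%:

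| b | Observed rates | Difference | OR | Power |
|---|---|---|---|---|
| 0 | 15% vs 10% | 5 points | 1.59 | 94% |
| 20% | 32% vs 28% | 4 points | 1.21 | 52% |
| 40% | 49% vs 46% | 3 points | 1.13 | 28% |
| 60% | 66% vs 64% | 2 points | 1.09 | 16% |

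Example at b = 40%: 1 − 0.85 × 0.60 = 0.49 and 1 − 0.90 × 0.60 = 0.46; OR = (0.49/0.51)/(0.46/0.54) = 1.13.

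With assumed true rates of 10% against 5%, power falls from 99% to 56%, 29% and 16% at the same backgrounds.

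**4. Strength of the glucose cue.** If chance agreement is taken as 50%, proportion correct = 0.5 + 0.5 × kappa. For 0.81 this is 0.905, or about 90% correct guesses in the pilot.

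**5. Texts side by side.** Section 3.2 keeps research midwives away from maternal glucose data. The Data Collection text has the site research team request a form on hyperglycaemia, hypoglycaemia and insulin changes, and has the research midwife abstract outcomes after discharge. No text says who reads the answers, whether the person issuing the form is someone other than the abstractor, or which form is completed first. The study table also places collection of birth and neonatal data at the post-birth visit, so the order is open rather than fixed the wrong way.

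**The case against.** - **The form may already handle recall.** It is an attachment that is not shown, and section 5.1 ties the questions to the period after trial medication. That phrase does not exclude post-operative symptoms, however, and the protocol text sets no window.
- **A reader might infer that drug effects are masked.** The documents do not support this. Only some items overlap with surgery, a common background dilutes a difference without removing it, and maternal glucose is recorded prospectively. The side effects named in section 7.1 are injection-site reactions and hyperglycaemia. The protocol claims no power for this outcome, and the rates above are assumed.
- **A reader might infer that allocation is revealed to the outcome collector.** The participant completes the form, and nothing says that the team reads it before neonatal data are entered. Other clues reach the team anyway: additional insulin, highest maternal glucose and pre-caesarean admission are secondary outcomes, and maternal medications after randomisation are recorded. The extra leakage from this form is not quantified. What stands is that it runs against the protocol's own safeguard.
- **A reader might infer that the primary outcome is biased.** It depends on nursery admission and respiratory support decided by postnatal clinicians and abstracted from records. Section 3.2 makes this argument, and pilot kappas for the surgeon, the staff receiving the baby and the ward staff were 0.24, 0.44 and 0.43.
- **Moving the form wholly before surgery would create a new gap.** With no minimum interval after the second injection, effects of that dose could be missed. This is a good objection to replacing the post-birth form, but not to adding an earlier entry.

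**Conclusion.** The point holds in limited form, as a cheap improvement. Both scheduled symptom questionnaires follow surgery, and the protocol states no pre-caesarean window. Non-specific symptoms in one secondary outcome can therefore be diluted towards no difference. For a true 15% against 10%, the illustration takes power from 94% to between 52% and 28% for backgrounds of 20% to 40%. This rests on assumed rates, on independence, and on women reporting post-operative symptoms as drug effects. The injection-specific, fetal-movement and glucose or insulin items are largely untouched.

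On blinding, sections 3.2 and 5.1 pull against each other. The consequence is a risk to blinded abstraction at the sites, of unknown size. It is neither a demonstrated unblinding nor a threat to the care decisions that generate the primary outcome.

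**What to change.** 1. Add a dated symptom entry, completed by the participant before the caesarean through the REDCap link she already receives at randomisation. Keep the post-birth form, and ask for each symptom whether it began before or after the caesarean, so that second-dose effects are still captured.
2. Hide the symptom, glucose and insulin answers from site staff who abstract outcomes. Have the neonatal outcome form completed and locked before those staff open the maternal symptom, glucose or insulin forms. The route by which women report high readings to clinical staff is not affected.
3. Reconcile the pilot-trial text in section 3.2 with the Data Collection text and study table in section 5.1, stating who issues the form, who may read it and when.

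The cost is one extra prompt before surgery with some non-response, a change to REDCap permissions and a data-entry order rule. No extra staff are needed. Case records may still hold some glucose or insulin clues, so the change reduces the exposure without removing it.
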